### **6.1. Endpoints: Healthy Subject Single and Multiple Ascending Dose Segments**

#### **6.1.1. Primary Endpoint(s) - Safety**

- *Vital signs (blood pressure, pulse rate, oral temperature).*
- *Physical examination findings over time.*
- *12-lead ECG parameters.*
- *Incidence and severity of treatment emergent adverse events and withdrawals due to treatment emergent adverse events.*
- *Incidence and magnitude of treatment emergent clinical laboratory abnormalities including hematology (with differentials), fibrinogen, chemistry, fasting glucose, lipids, urinalysis.*
- *Change in 24 hour creatinine clearance from Day -1 and Day 10 (MAD only).*

### 6.1.2. Secondary Endpoint(s)

Systemic pharmacokinetics parameters (defined in Section 9.3.1 of the protocol) will include:

- *Single Dose:*  $C_{max}$ ,  $T_{max}$ ,  $AUC_{inf}$ ,  $AUC_{last}$ ,  $AUC_{24}$ ,  $C_{max(dn)}$ ,  $AUC_{inf(dn)}$ ,  $AUC_{last(dn)}$ ,  $t_{1/2}$ ,  $MRT$ ,  $V_z/F$ , and  $CL/F$  (if data permit).
- *Multiple Dose:*
- *Day 1:*  $C_{max}$ ,  $T_{max}$ ,  $AUC_{tau}$  ( $tau=12$  or  $24$  hours),  $C_{max(dn)}$ ,  $AUC_{tau(dn)}$ .
- *Day 10:*  $C_{max}$ ,  $T_{max}$ ,  $AUC_{tau}$  ( $tau=12$  or  $24$  hours),  $C_{max(dn)}$ ,  $AUC_{tau(dn)}$ ,  $t_{1/2}$ ,  $C_{min}$ ,  $C_{av}$ ,  $R_{ac}$ ,  $R_{ac,C_{max}}$ ,  $PTR$ ,  $MRT$ ,  $V_z/F$ ,  $CL/F$  (if data permit).
- *Urinary Pharmacokinetics (defined in Section 9.3.1 of the protocol; for healthy subjects, multiple ascending dose period only):*  $Ae_{tau}$  and  $Ae_{tau}\%$ ,  $CL_r$  (if data permit).

CCI

[Redacted content]

## 6.2. Endpoints: Psoriasis Multiple Dose Cohorts

*All subjects who receive at least one dose of randomized study medication, and have a baseline and at least one post-baseline measurement (after taking randomized study medication) will be included in the efficacy data analyses for the psoriasis cohorts.*

### 6.2.1. Primary Endpoint(s) – Safety

- *Vital signs (blood pressure, pulse rate, and oral temperature).*
- *Physical examinations findings over time.*
- *12-lead ECG parameters.*
- *Incidence and severity of treatment emergent adverse events and withdrawals due to treatment emergent adverse events.*
- *Incidence and magnitude of treatment emergent clinical laboratory abnormalities including hematology (with differentials) chemistry, fasting glucose, lipids, urinalysis.*

### 6.2.2. Secondary Endpoints

- *Multiple Dose (defined in Section 9.3.1 of the protocol):  $C_{max}$ ,  $T_{max}$ ,  $AUC_{tau}$ ,  $C_{max}(dn)$ ,  $AUC_{tau}(dn)$ ,  $t_{1/2}$ , PTR,  $C_{min}$ ,  $C_{av}$ , MRT,  $V_z/F$  and CL/F (if data permit).*
- *Change from baseline in psoriasis area and severity index (PASI) score at Day 28.*

CCI

[Redacted content]

### **6.3.1. Adverse Events**

Any events occurring following start of the treatment or increasing in severity will be counted as treatment emergent.

Events that occur in a non-treatment period (for example, washout or follow-up) will be counted as treatment emergent and attributed to the previous treatment taken.

### **6.3.2. Laboratory Safety Tests**

Safety laboratory tests will be performed as described in the protocol.

To determine if there are any clinically significant laboratory abnormalities, the haematological, clinical chemistry (serum) and urinalysis safety tests will be assessed against the criteria specified in the sponsor reporting standards. The assessment will take into account whether each subject's baseline test result is within or outside the laboratory reference range for the particular laboratory parameter.

### **6.3.3. Vital Signs**

For subjects in study Periods 1 to 2, in each cohort, single supine measurements will be taken at times detailed in the Schedule of Activities given in the protocol.

The following vital signs endpoints will be determined:

- The maximum decrease and increase from baseline (pre-dose) over all measurements taken post-dose for supine systolic and diastolic blood pressures.

The maximum increase from baseline will be calculated by first subtracting the baseline value from each post-dose measurement to give the change from baseline. The maximum of these values over the respective period will then be selected, except in the case where a subject does not show an increase. In such an instance, the minimum decrease should be taken.

Similarly, the maximum decrease from baseline will be determined by selecting the minimum value of the changes from baseline. In cases where a subject does not show a decrease, the minimum increase should be taken.

### **6.3.4. ECG**

12-lead ECGs will be recorded in triplicate for subjects in Periods 1 to 2 at times detailed in the Schedule of Activities given in the protocol.

A single 12-lead ECG will be obtained on all subjects at screening and follow-up as well as on selected visits as detailed in Schedule of Activities section of the Protocol.

The QT, QTc, PR, RR, QRS and heart rate will be recorded at each assessment time.

If not supplied, QTcF will be derived using Fridericia’s heart rate correction formula:

$$QTcF = QT / (RR)^{1/3} \quad \text{where } RR = 60/HR \text{ (if not provided)}$$

If not supplied, QTcB will be derived using Bazett’s heart rate correction formula:

$$QTcB = QT / (RR)^{1/2} \quad \text{where } RR = 60/HR \text{ (if not provided)}$$

The average of the triplicate readings collected at each assessment time will be calculated for each ECG parameter. Baseline will be defined as the average of the triplicate predose recordings in each study period.

The maximum absolute value (post-dose) and the maximum increase from baseline for QTcF, QT, heart rate, PR and QRS, will be determined over all measurements taken postdose for QTcF, PR and QRS.

The maximum increase from baseline will be calculated by first subtracting the baseline value from each post-dose measurement to give the change from baseline. The maximum of these values over the respective period will then be selected, except in the case where a subject does not show an increase. In such an instance, the minimum decrease should be taken.

### 6.3.5. Other Safety Data

Additional safety data will be collected as described in the protocol and will be listed if collected in the sponsor’s database.

### 6.4. Pharmacokinetic Endpoints

Blood and urine samples for PK analysis of PF-06826647 will be taken according to the Schedule of Activities given in the protocol.

The following PK parameters will be calculated for PF-06826647 (if possible) from the plasma concentration-time data using standard noncompartmental methods:

	Parameter	Definition	Method of Determination
Plasma	$AUC_{last}$	Concentration-time profile from time zero to the time of the last quantifiable concentration ( $C_{last}$ )	Linear/Log trapezoidal method
	$AUC_{\tau}$	Area under the plasma concentration-time profile over the dosing interval $\tau$	Linear/Log trapezoidal method
	$AUC_{inf}^a$	Area under the plasma concentration-time profile from time zero extrapolated to infinite time	$AUC_{last} + (C_{last}^*/k_{el})$ , where $C_{last}^*$ is the predicted plasma concentration at the last quantifiable time point estimated from the log-linear regression analysis
	$C_{max}$	Maximum plasma concentration	Observed directly from data

	Parameter	Definition	Method of Determination
	$C_{min}$	Lowest concentration observed during dosing interval, $\tau$ ; if measured at end of dosing interval, equivalent to $C_{trough}$	Observed directly from data
	$C_{av}$	Average concentration at steady state	$C_{av} = AUC_{\tau,ss}/\tau$
	$T_{max}$	Time for $C_{max}$	Observed directly from data as time of first occurrence
	$t_{1/2}^a$	Terminal elimination half-life	$\text{Log}_e(2)/k_{el}$ , where $k_{el}$ is the terminal phase rate constant calculated by a linear regression of the log-linear concentration-time curve. Only those data points judged to describe the terminal log-linear decline will be used in the regression
	$CL/F^a$	Apparent clearance	Dose/ $AUC_{inf}$ for SD Dose/ $AUC_{\tau}$ for MD
	$V_z/F^a$	Apparent volume of distribution	Dose/( $AUC_{inf} \cdot k_{el}$ ) for SD Dose/( $AUC_{\tau} \cdot k_{el}$ ) for MD
	$Rac$	Observed accumulation ratio based on AUC	$AUC_{\tau}(ss)/AUC_{\tau}(sd)$
	$Rac, C_{max}$	Observed accumulation ratio based on $C_{max}$	$C_{max}(ss)/C_{max}(sd)$
	$PTR$	Peak to Trough ratio	$C_{max,SS}/C_{min,SS}$
	$MRT$	Mean residence time	$AUMC_{inf}/AUC_{inf}$ where $AUMC_{inf}$ is the area under the first moment curve from time zero to infinity.
	$C_{max}(dn)$	Dose normalized $C_{max}$	$C_{max}/Dose$
	$AUC_{last}(dn)$	Dose normalized $AUC_{last}$	$AUC_{last}/Dose$
	$AUC_{inf}(dn)^a$	Dose normalized $AUC_{inf}$	$AUC_{inf}/Dose$
Urine	$Ae_{\tau}$	Cumulative amount of drug recovered unchanged in urine from 0 to dose interval ( $\tau$ ) hours post-dose	Sum of [urine concentration * sample volume] for each collection interval
	$Ae_{\tau}\%$	Percent of dose recovered unchanged in urine from 0 to dose interval ( $\tau$ ) hours post-dose	$Ae_{\tau}/Dose * 100$
	$CLr$	Renal clearance	$Ae_{\tau}/AUC_{\tau}$

a If data permit

The PK parameters will be summarized descriptively by dose, regimen and study population (healthy subject and psoriasis subject) in accordance with Pfizer data standards. Summary statistics will also include the geometric mean and coefficient of variation for all parameters except  $T_{max}$ .

Dose normalized (to 1 mg) AUC and  $C_{max}$  values of PF-06826647 will be plotted against dose (using a logarithmic scale if dose range is greater than 10-fold) for single- and multiple dose phases, and will include individual subject values and the geometric means for each dose. These plots will be used to help understand the relationship between the plasma PK parameters and dose. Additional PK analyses may be performed if deemed appropriate.

Urine amounts of PF-06826647 and CLr will be listed and summarized descriptively, if data permits.

CCI [REDACTED] (fasted) will be used as Reference and  $AUC_{24}$  and  $C_{max}$  on Day 1 in MAD (QD) period (fed) as Test. Natural log transformed  $AUC_{24}$  and  $C_{max}$  will be analyzed using a mixed effect model with treatment (Dose levels) and period as a fixed effect and subjects within a treatment as a random effect. Estimates of the adjusted mean differences (Test-Reference) and corresponding 90% confidence intervals will be obtained from the model. The adjusted mean differences and 90% confidence for the differences will be exponentiated to provide estimates of the ratio of adjusted geometric means (Test/Reference) and 90% confidence intervals for the ratios.

CCI [REDACTED]  
[REDACTED]

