Preliminary pharmacokinetic data on Day 1 and Day 10 following multiple oral administration of PF-06826647 with standard meal at 30, 100 and 400 mg once daily (QD) are summarized in Table 2. By contrast with the PK parameters reported in Table 1, single dose administration with standard meal modestly increased the exposure of PF-06826647 by approximately 1.6 and 1.5 fold for AUC and Cmax, respectively at 400 mg. The increase in exposure at steady state appears to be less than proportional with increase in dose. Multiple dosing over 10 days achieved steady state with modest accumulation (1.3 and 1.2 fold for AUC and Cmax at 400 mg, respectively).

**Table 2. Preliminary Summary of Draft Plasma PK Parameters of PF-06826647 Following Multiple Oral QD Dose Administration of PF-06826647 for 10 Days in Healthy Subjects (Fed-Standard Meal)**

Dose (mg)	Day 1		Day 10		
	C max (ng/mL)	AUC 24 (ng.hr/mL)	C max (ng/mL)	AUC 24 (ng.hr/mL)	t 1/2 hr
30	84 (24)	664 (25)	85 (27)	752 (32)	9 (67)
100	267 (20)	1811 (23)	263 (30)	1950 (34)	7 (38)
400*	520 (30)	3488 (58)	689 (14)	4919 (32)	4(13)

Geometric mean (%CV) for all except arithmetic mean (%CV) for t1/2; Abbreviations: %CV = percent coefficient of variation; NR = Not Reportable. AUC24= Area under the concentration-time curve from time zero to 24 hours post single dose; Cmax = Peak plasma concentration; \*Partial data (only 4 subjects up to Day 11).

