### 3.1.1. Healthy Subject Single and Multiple Ascending Dose Periods

In the combined single ascending and multiple ascending dose (SAD/MAD) healthy subject cohorts there will be approximately 8 subjects per dose level; 6 subjects will receive PF-06826647 and 2 subjects will receive placebo per the randomization code.

Healthy subjects will be randomized (once) into the SAD period, at which time, they will receive treatment assignment (active PF-06826647 dose level or placebo) for both the SAD and MAD periods. Subjects will receive the same blinded treatment assignment (ie, the same dose level of active PF-06826647 or placebo) throughout in both the SAD (Period 1) and MAD (Period 2) periods.

During the single ascending dose (SAD) period, healthy subjects in Cohort 1 to Cohort 6 will receive single doses of 3, 10, 30, 100, 400, or 1600 mg of PF-06826647 or placebo in a dose escalation format as shown in the Study Schema ([Figure 1](#)). The doses and meal condition of optional cohorts (Cohort 7 and Cohort 8) will be decided on emerging PK, CCI and safety data from prior SAD and MAD cohorts. Dose escalation to subsequent cohorts will be based on a minimum of 3 days of safety data and PK over 24 hours in a minimum of 6 subjects enrolled in a cohort. Subjects will reside in the clinical research unit (CRU) for the single ascending dose phase from Day -1 until completion of protocol assessments on Day 4. Dosing occurs on Day 1. Subjects will return to the unit on Day 8 ( $\pm 1$ ) day for the end of single dose period assessment and PK sample.

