At least 14 days (minimum wash-out period) will separate the beginning of the single and multiple dose periods (ie, at least 14 days will separate the single dose administered in the SAD and the first QD dose in the MAD); however, the minimum wash-out period may be adjusted based on emerging PK data. Based on the PK predictions and emerging PK data from this study, the currently planned starting dose in the MAD period is 30 mg (previously, a PF-06826647 starting dose of 10 mg was planned for the MAD period under the original protocol) is not expected to provide pharmacologically relevant exposure. In the multiple ascending dose (MAD) period, healthy subjects in Cohort 3 to Cohort 6 in Period 2 will receive doses of 30, 100, 400, or 1200 mg QD of PF-06826647 or placebo for 10 days (Day 1 through Day 10) with standard meal. The dose of Cohort 6 in MAD (Period 2) may be adjusted based on emerging data from earlier MAD cohorts in the trial. Subjects will be housed for the duration of the multiple dosing period, discharged on the morning of Day 14. Subjects will return for outpatient visits on morning of Day 17 for PK sample collection and Day 28 ( $\pm 3$  days) for end of study procedures. Based on emerging PK data, subject may be asked to return between Day 17 and Day 28 for an additional outpatient visit for PK sample

collection. The additional PK sample will allow characterization of terminal half-lives at higher dose cohorts.

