- a listing of all concentrations sorted by subject ID, cohort, dose and nominal time post-dose. The concentration listing will also include the actual times. Deviations from the nominal time will be given in a separate listing.
- a summary of concentrations by cohort, dose and nominal time post-dose, where the set of statistics will include n, mean, median, standard deviation, coefficient of variation (cv), minimum, maximum and the number of concentrations above the lower limit of quantification.
- median concentrations time plots (on both linear and semi-log scales) against nominal time post-dose by cohort and dose (all treatments on the same plot per scale, based on the summary of concentrations by cohort, dose and time post-dose).
- Median concentration time plots (on both linear and semi-log scales) against nominal time post-dose by meal condition and dose for Day 1 (0-24 h post dose) for Cohort 3, 4 and 5 (30, 100 and 400 mg cohorts).
- Boxplot of dose-normalized  $AUC_{24}$  and  $C_{max}$  on Day 1 in SAD and MAD separately by dose group and meal condition for Cohorts 3, 4 and 5.
- mean concentrations time plots (on both linear and semi-log scales) against nominal time post-dose by cohort and dose (all treatments on the same plot per scale, based on the summary of concentrations by cohort, dose and time post-dose).
- individual concentration time plots by cohort and dose (on both linear and semi-log scales) against actual time post-dose (there will be separate spaghetti plots for each dose per scale).
- individual concentration time plots by subject (on both linear and semi-log scales) against actual time post-dose [there will be separate plots for each subject (containing all doses) per scale].

The length of time used for the x-axes of these plots will be decided on review of the data, and will depend on how long PF-06826647 concentration is quantifiable in the matrix.

For summary statistics, median and mean plots by sampling time, the nominal PK sampling time will be used, for individual subject plots by time, the actual PK sampling time will be used. All statistical analyses related to the CCI will be performed as stated in Section 6.4.

CCI [Redacted]

CCI [Redacted]

[Redacted]

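### The fed-versus-fasted model gives one meal ratio each for AUC24 and Cmax; by-dose ratios should be added, because preliminary data suggest (without establishing) that the effect differs by dose

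*SAP*

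**What the plan says.** SAP 6.4 takes Day 1 of the multiple-dose period (fed) as Test and a fasted condition as Reference. The text that defines the Reference is largely redacted. Log AUC24 and log Cmax go into a "mixed effect model with treatment (Dose levels) and period as a fixed effect and subjects within a treatment as a random effect", and the differences are "exponentiated to provide estimates of the ratio of adjusted geometric means (Test/Reference) and 90% confidence intervals for the ratios". Protocol 9.3.1 lists the same terms.

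Protocol 3.1.1 plans single fasted doses that include 30, 100 and 400 mg in Cohorts 3 to 5. In the multiple-dose period, Cohorts 3 to 6 receive "30, 100, 400, or 1200 mg QD of PF-06826647 or placebo for 10 days" with a standard meal. Per dose level, "6 subjects will receive PF-06826647 and 2 subjects will receive placebo per the randomization code".

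Protocol 1.3.2 reports that "single dose administration with standard meal modestly increased the exposure of PF-06826647", by about 1.6-fold for AUC and 1.5-fold for Cmax at 400 mg. The footnote to the 400 mg row of Table 2 reads "Partial data (only 4 subjects up to Day 11".

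SAP 8.3.1.1 already plans PK summaries by regimen and period. It also plans median profiles by meal condition and dose, and boxplots of dose-normalised AUC24 and Cmax "on Day 1 in SAD and MAD separately by dose group and meal condition for Cohorts 3, 4 and 5".

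**The concern.** Fasted dosing belongs to the single-dose period and fed dosing to the multiple-dose period, so the period term carries the meal effect. With dose and period as main effects only, the fitted fed/fasted ratio is the same at every dose by construction. The visible text has no check of that assumption and no ratio with an interval by dose.

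The geometric means in the protocol rise unevenly between fasted and fed conditions, most at the higher doses. If that pattern is real, one average ratio overstates the meal effect at 30 mg and understates it at 400 mg. The 400 mg level is of particular interest because the first psoriasis cohort takes it with a standard meal in order to raise exposure (Protocol 1.3.4.1). At stake is how well the meal effect is described at that dose.

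**Working it through.** **Inputs.** Protocol 1.3.2, Table 1 (single dose, fasted) and Table 2, Day 1 (fed). Entries are geometric means with %CV.

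| Dose | AUC24 fasted | AUC24 fed | Cmax fasted | Cmax fed |
|---|---|---|---|---|
| 30 mg | 543 (49) | 664 (25) | 78 (34) | 84 (24) |
| 100 mg | 1160 (55) | 1811 (23) | 167 (55) | 267 (20) |
| 400 mg | 1933 (28) | 3488 (58) | 329 (28) | 520 (30) |

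**1. The protocol's own 400 mg figures.** The text gives about 1.6 (AUC) and 1.5 (Cmax). Like for like, the tables give 3488/1933 = 1.80 and 520/329 = 1.58, so the stated figures are not reproduced. Fed AUC24 over fasted AUClast, 3488/2135 = 1.63, would round to 1.6 but mixes two metrics. A matched subset of subjects could also explain it, but the documents do not say so.

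**2. Ratios by dose.**
- AUC24: 664/543 = 1.22; 1811/1160 = 1.56; 3488/1933 = 1.80.
- Cmax: 84/78 = 1.08; 267/167 = 1.60; 520/329 = 1.58.

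AUC24 rises across all three doses. Cmax rises from 30 to 100 mg and is then flat.

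**3. What an additive model would report.** With equal numbers per dose, it is approximately the geometric mean of the by-dose ratios.
- AUC24 with the tabulated 400 mg ratio: (1.223 × 1.561 × 1.804)^(1/3) = 1.51. Then 1.51/1.223 = 1.24 (24% above 30 mg) and 1.51/1.804 = 0.84 (16% below 400 mg).
- AUC24 with the stated 1.6: (1.223 × 1.561 × 1.6)^(1/3) = 1.45. Then 1.45/1.223 = 1.19 (19% above) and 1.45/1.6 = 0.91 (9% below).
- Cmax from the tables: (1.077 × 1.599 × 1.581)^(1/3) = 1.40.

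Weighting the tabulated 400 mg ratio by its four subjects, against six at each other dose, moves the AUC24 value from 1.51 to 1.48.

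**4. How strong is the evidence of a difference?** The ratio of ratios, 400 against 30 mg, is 1.804/1.223 = 1.48 for AUC24 and 1.581/1.077 = 1.47 for Cmax. For a rough 90% CI, take v = ln(1 + CV²) and, at each dose, variance = (v_fasted + v_fed − 2ρ√(v_fasted × v_fed))/n. Use n = 6 at 30 mg (assumed, as planned) and n = 4 at 400 mg. The documents give no within-subject correlation ρ, so a range is shown.

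Example, AUC24 at ρ = 0: (0.215 + 0.061)/6 + (0.075 + 0.290)/4 = 0.137, so SE = 0.371 and exp(1.645 × 0.371) = 1.84. The interval is 1.48 times or divided by 1.84.

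| ρ (assumed) | AUC24, 1.48 | Cmax, 1.47 |
|---|---|---|
| 0 | 0.80–2.71 | 0.96–2.25 |
| 0.5 | 0.92–2.36 | 1.08–1.99 |
| 0.8 | 1.03–2.11 | 1.20–1.79 |

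For AUC24 the interval includes 1 at the two lower correlations. For Cmax it includes 1 only at ρ = 0. A normal multiplier with 4 to 6 subjects makes all of these somewhat too narrow.

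**5. Cost in precision.** Assume n = 6 per dose and a within-subject CV of 20 to 30%, so s = √ln(1 + CV²) = 0.198 to 0.294.
- By dose: SE = s√(2/6) = 0.114 to 0.169. With t = 1.753 (15 df), the 90% CI is the estimate times or divided by 1.22 to 1.35.
- Pooled: SE = s√(2/18) = 0.066 to 0.098. With t = 1.740 (17 df), the factor is 1.12 to 1.19.

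**The case against.** The strongest reply is that a common ratio is a defensible exploratory choice with about six active subjects per dose, and that the tables are too weak to reject it. Much of this stands. Both tables are labelled preliminary and draft. The 1.80 comes from four subjects with an AUC24 CV of 58%. Cmax does not rise from 100 to 400 mg. At the stated 1.6, the AUC ratio is nearly flat above 100 mg (1.56). Even with six subjects and a 30% CV, the by-dose intervals overlap: 1.22 times or divided by 1.35 is 0.90 to 1.65, and 1.80 times or divided by 1.35 is 1.33 to 2.43. A reader might infer that the tables contradict a common ratio; they do not go that far.

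The mechanism is also inference. The protocol describes low solubility (1.2.5) and predicts falling bioavailability at higher doses (1.3.3.1), but nowhere says that the meal effect grows with dose. Fasted AUC24 rises 9321/1933 = 4.8-fold for a 4-fold dose step from 400 to 1600 mg. The 400 mg fasted mean may therefore be low by chance, which would inflate the 1.80.

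Three further readings are tempting and not supported:
- **That the pooled interval is wrong.** It is narrower because it estimates an average over doses. That is not an error.
- **That the model mixes Cohort 6 (1600 mg fasted, 1200 mg fed) into the ratio.** The text next to the model is redacted and may name the cohorts. The companion displays are limited to Cohorts 3 to 5.
- **That a psoriasis dose depends on the pooled ratio.** Protocol 1.3.4.1 bases the 400 mg margins on observed steady-state exposure, and PK is measured directly in psoriasis subjects.

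The planned plots and summaries also mean that the dose pattern is not hidden. What they do not give is a within-subject fed/fasted ratio with a 90% CI at each dose. Uncertainty about whether the ratio is constant is a reason to show it by dose.

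**Conclusion.** The structural point holds: the visible model terms give one fed/fasted ratio for AUC24 and one for Cmax, assumed equal across doses. The preliminary data suggest a difference by dose and do not establish it. With equal weights, the pooled AUC24 ratio would be about 1.45 to 1.51, which is 19 to 24% above the 30 mg ratio and 9 to 16% below the 400 mg ratio. The spread reflects whether the 400 mg figure is the stated 1.6 or the tabulated 1.80, a mismatch that the protocol should resolve.

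This rests on draft geometric means that may not come from the same subjects in both periods, and on reading the unredacted model sentence as complete. Redacted text nearby could add by-dose analyses. The comparison is exploratory, so this is a cheap improvement to reporting and not a flaw that undermines a study conclusion.

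**What to change.** In SAP 6.4, with matching text in Protocol 9.3.1:
- Add a dose-by-period term to the fed-versus-fasted model.
- State that the comparison uses Cohorts 3 to 5 (30, 100 and 400 mg), in line with the planned meal-condition plots.
- Report the fed/fasted ratio with its 90% CI at each of the three doses beside the pooled ratio, for AUC24 and for Cmax, and label them exploratory.
- In Protocol 1.3.2, reconcile the stated 400 mg ratios (about 1.6 and 1.5) with Tables 1 and 2 (1.80 and 1.58), naming the AUC metric and the subjects used.

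The cost is one model term and three extra rows per parameter, with no new data. The downside is wider by-dose intervals: times or divided by about 1.22 to 1.35, against 1.12 to 1.19 pooled, under the assumed six subjects per dose and within-subject CV of 20 to 30%. The pooled ratio remains available from the additive model.
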